In the SAD portion of Study AACC, it was observed that LY3002813 had a significantly shorter half-life than the approximately 24-day half-life predicted based on data from nonclinical studies (a prediction that was consistent with the expected half-life of an immunoglobulin G1 antibody [Lobo et al. 2004]). After single-dose administration from 0.1 mg/kg to 3.0 mg/kg, the mean terminal elimination half-life was approximately 4 days, increasing to approximately 10 days (243 hours) at the 10-mg/kg dose level. The PK of a single dose of 1.0 mg/kg IV LY3002813 in young, healthy subjects was indistinguishable from the PK in AD patients at the same dose level. In the MAD phase, most patients at dose levels \leq 3 mg/kg had serum LY3002813 concentrations below the limits of detection 28 days after dosing; patients receiving 10 mg/kg did have sustained quantifiable concentrations 28 days after dosing.

Greater than 90% of the patients with AD had treatment-emergent antidrug antibodies (ADAs) 3 months after the first dose at all dose groups; titers tended to increase by the end of the MAD phase and persist 3 months after the last dose. Dosing was stopped in the MAD phase of Study AACC because of high prevalence of ADAs and unexpected rapid elimination of the study drug.

Sixteen adverse events (AEs) of mild or moderate infusion related reactions were reported in 6 of 51 patients dosed with LY3002813. Infusion reactions occurred in 1 patient in the 0.3-mg/kg cohort, 2 patients in the 1.0-mg/kg cohort, and 3 patients in the 3.0-mg/kg cohort. The infusion reactions developed in 1 of the 6 patients after the first MAD dose and in 5 of the 6 patients after the second MAD dose. One patient discontinued because of dyspnea due to an infusion reaction (mild severity). All patients with infusion reactions had high peak titers of ADAs. Three patients were rechallenged with premedication (acetaminophen, antihistamine, and/or hydrocortisone) and had milder reactions on rechallenge. Infusion reactions began during the infusion or within 30 minutes of completing the infusion and lasted between 1 minute and 8 hours. Symptoms included chills/shivering (3 patients); flushing (2 patients); hypotension (asymptomatic, 1 patient); dyspnea (1 patient); myalgia (1 patient); rash (1 patient); and fever (1 patient).

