7.1. Summary of Study Design

[figure not shown]
This is a Phase 1b, patient- and investigator-blind, randomized within cohort, placebo-controlled, parallel-group, single- and multiple-dose study in patients with MCI due to AD or mild to moderate AD to assess the safety, tolerability, PK, and PD of single and multiple IV doses of LY3002813.

This study (Study AACD) will enroll patients with MCI due to AD, mild AD, or moderate AD with amyloid deposition confirmed by florbetapir PET imaging using National Institute on Aging-Alzheimer's Association (NIAAA) work group consensus guidelines (Albert et al. 2011; McKhann et al. 2011). This study will be conducted at sites in multiple countries, including the United States and Japan. Up to 150 patients may be enrolled so that approximately 72 patients (7 dosing cohorts of 8 to 12 patients) complete the study.

[figure not shown]
The study will be conducted in at least 7 cohorts ([Figure AACD.7.1](#)):

- Cohort 1: 10 mg/kg IV single dose
- Cohort 2: 20 mg/kg IV single dose
- Cohort 3: 40 mg/kg IV single dose
- Cohort 4: 10 mg/kg IV every 2 weeks (Q2W) for 24 weeks
- Cohort 5: 20 mg/kg IV Q2W for 24 weeks
- Cohort 6: 10 mg/kg IV Q4W for up to 72 weeks
- Cohort 7: 20 mg/kg IV Q4W for up to 72 weeks

[figure not shown]
Part A: Single dose; 72-week follow-up (Cohorts 1 & 2), 24-week follow-up (Cohort 3)

Part B: 24-weeks, Q2W multiple dose treatment; 48-week follow-up

Part C: Chronic dose, 72-week, Q4W multiple dose treatment; 12-week follow-up

Abbreviations: f/u = follow up; IV = intravenous; MRI = magnetic resonance imaging; PET = positron emission tomography; Q2W = every 2 weeks; Q4W = every 4 weeks; x = times.

Assessments: A = amyloid PET; I = immunogenicity; M = MRI; T = tau PET; C = cognition; F = cerebrospinal fluid.

D = dosing; S = 4 week safety review of Cohort 2.

Follow-up assessments (immunogenicity, I; MRI, M) 12 weeks after last dose for Cohorts 6 and 7.

Note: vertical lines indicate 4-week intervals. Additional immunogenicity assessments will be performed every 12 weeks up to 48 weeks after the last dose of LY3002813 if the antibody titer has not returned to baseline.

Figure AACD.7.1. Study design.

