7.1.3. Part A: Single Dose Cohorts (Cohorts 1 through 3)

Safety, PK, and PD will be assessed in Cohorts 1 through 3 after single doses of LY3002813 or placebo. The planned doses are 10, 20, and 40 mg/kg IV for Cohorts 1, 2, and 3, respectively; with 8 patients (6 LY3002813; 2 placebo) planned to be enrolled in each cohort. Dose escalation will only occur after the safety from the preceding cohort has been established in at least 4 patients receiving LY3002813 and 1 receiving placebo. Safety data will be collected at least 1 week after dosing for dose escalation to Cohort 2 and at least 4 weeks after dosing for dose escalation to Cohort 3. Enrollment in Cohorts 2 and 3 will only commence once enrollment into the preceding cohort has completed. Safety, PK, and PD will be assessed at regular intervals for approximately 72 weeks (in Cohorts 1 and 2) or 24 weeks (in Cohort 3) after starting the dosing with study drug ([Attachment 1](#)).

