10.4.1. Additional Immunogenicity and Safety Visits for all Cohorts

If the immunogenicity titer at the last scheduled assessment or discontinuation visit is positive, then additional safety assessments (concomitant medications, AEs, laboratory values, vital signs, ECGs) and samples for immunogenicity and PK should be taken every 12 weeks until the titer returns to baseline (comes within a single 2-fold dilution of the baseline titer) or up to 48 weeks after the last dose of LY3002813 if the antibody titer has not returned to baseline within 48 weeks after the last dose. In the case of a patient whose result is positive at baseline with a 1:10 titer and then subsequently develops a treatment-emergent ADA response that increases to much higher titers, the antibody titer would need to decline to a titer of 1:20 or less to be considered a “return to baseline.” In contrast, if the patient’s result is “not detected” at baseline (in an assay with a 1:10 minimal required dilution), the titer would need to decline to either “detected” with a 1:10 titer or a result of “not detected” to be considered a “return to baseline.”

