### **4.2.7. Safety Analyses**

#### **4.2.7.1. Clinical Evaluation of Safety**

All investigational product and protocol procedure AEs will be listed. At a minimum, all safety data will be summarized using descriptive methodology.

The incidence of symptoms for each IV dose will be presented by severity and by association with investigational product, as perceived by the investigator. Symptoms reported to occur before randomization will be distinguished from those reported as new or increased in severity during the study. Each symptom will be classified by the most suitable term from the medical regulatory dictionary.

The number of investigational product-related SAEs will be reported.

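### In Cohorts 3, 6 and 7, and for early discontinuers, antibody-triggered visits can lengthen AE observation for titre-positive patients, and the by-dose AE tables have no cut-off to keep groups comparable

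*SAP*

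**What the plan says.** SAP 4.2.7.1 defines the main AE tables: "The incidence of symptoms for each IV dose will be presented by severity and by association with investigational product, as perceived by the investigator". It separates symptoms that predate randomization from those that arise or worsen on study. It sets no last date on which an event still counts, and no adjustment for time observed. SAP 4.4 uses TEAE for the registry tables without defining its window. Protocol 11.2.7.1 adds no cut-off either.

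Protocol 10.4.1, repeated in footnote s of Attachment 1, applies when the titre is still positive at the final scheduled visit or at discontinuation. Then "additional safety assessments (concomitant medications, AEs, laboratory values, vital signs, ECGs) and samples for immunogenicity and PK should be taken every 12 weeks". These visits stop when the titre is back to baseline, or run "up to 48 weeks after the last dose of LY3002813 if the antibody titer has not returned to baseline within 48 weeks". The rule is not tied to treatment arm. On how often it may be triggered, Protocol 5.1 reports from Study AACC: "Greater than 90% of the patients with AD had treatment-emergent antidrug antibodies (ADAs) 3 months after the first dose at all dose groups".

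Scheduled follow-up also differs within Part A. Protocol 7.1.3 gives "approximately 72 weeks (in Cohorts 1 and 2) or 24 weeks (in Cohort 3) after starting the dosing with study drug".

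SAP 4.2.3 combines placebo within each study Part for the baseline table. No grouping is stated for the AE tables. The SAP was approved in December 2015 and protocol amendment (f) in December 2017. The note to the SAP's design figure mentions only extra immunogenicity assessments when titres are rising, and does not mention AEs.

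**The concern.** Crude incidence rises with time under observation. If one group is watched longer because of a post-treatment result that the drug itself tends to cause, its AE percentage goes up with no drug effect on AEs. Safety is a secondary objective, and Protocol 5.2 makes the safety profile part of the decision on further development, so the by-dose AE tables will be read as comparisons even though they are descriptive.

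There is a second problem that does not depend on antibodies. The highest single dose is scheduled for one third of the follow-up of the two lower single doses. Side by side, crude incidence would make it look safer.

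**Working it through.** **Follow-up and room for extension.** Days are from the Attachment 1 schedules. Follow-up after last dose = (last visit day − last dose day)/7. Maximum extension = max(0, 48 − follow-up).

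| Cohorts | Last dose | Last scheduled visit | Follow-up after last dose (weeks) | Maximum extension (weeks) |
|---|---|---|---|---|
| 1-2 | Day 1 | V17, Day 505 | (505−1)/7 = 72 | 0 |
| 3 | Day 1 | V13, Day 169 | (169−1)/7 = 24 | 48−24 = 24 (2 visits) |
| 4-5 | Day 169 | V22, Day 505 | (505−169)/7 = 48 | 0 |
| 6-7 | Day 505 | V27, Day 589 | (589−505)/7 = 12 | 48−12 = 36 (3 visits) |

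The fourth column reproduces the 72, 24, 48 and 12 weeks in Protocol 7.1. Three of seven cohorts can be affected among completers: 8+12+12 = 32 of 72 planned completers, of whom 6+9+9 = 24 of 54 are on active drug. A patient in any cohort who discontinues less than 48 weeks after the last dose can also be extended.

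In Part C the cap counts from the last LY3002813 dose, so an early switch to placebo infusion (Protocol 7.1.5) shortens the extension. A last active dose at Week 48 gives 48+48−84 = 12 weeks; at Week 36 it gives 36+48−84 = 0. A placebo patient has no LY3002813 dose, so the cap is undefined there; the check uses the same calendar limit.

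**Effect on crude incidence.** Assume the same constant AE hazard in both arms. Let p be incidence by the last scheduled visit (T1), T2 the maximum extended time, and q the share extended to T2:

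incidence = (1−q)·p + q·[1 − (1−p)^(T2/T1)]

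For Cohort 3, T2/T1 = 48/24. With p = 30% and q = 0.9: 0.1×0.30 + 0.9×(1−0.7²) = 0.030 + 0.459 = 48.9%. For Part C, T2/T1 = 120/84: 0.1×0.30 + 0.9×0.399 = 38.9%.

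| Positive to cap, active / placebo | Cohort 3 active vs placebo | Part C active vs placebo |
|---|---|---|
| 90% / 0% | 48.9% vs 30.0% | 38.9% vs 30.0% |
| 50% / 0% | 40.5% vs 30.0% | 35.0% vs 30.0% |
| 50% / 10% | 40.5% vs 32.1% | 35.0% vs 31.0% |

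The AACC figure is above 90%; at 100% / 0% the active values are 51.0% and 39.9%. In the first row mean observation is 24+0.9×24 = 45.6 against 24 weeks in Cohort 3 (ratio 1.90), and 84+0.9×36 = 116.4 against 84 weeks in Part C (ratio 1.39).

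**Single-dose comparison.** At the hazard giving 30% by Week 24, incidence by Week 72 is 1−0.7³ = 65.7%. Cohorts 1-2 would show 65.7% beside 30.0% for an unextended Cohort 3, with no dose effect.

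Placebo combined across Part A, with two patients per cohort, has mean scheduled follow-up (72+72+24)/3 = 56 weeks. Its expected incidence is (65.7+65.7+30.0)/3 = 53.8%. Cohort 3 active lies below that with no extension (30.0%) and with 90% extended to the cap (48.9%).

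**The case against.** The strongest reply is that these are descriptive Phase 1b tables with 2-3 placebo patients per cohort, no AE hypothesis test, and a listing of product and procedure AEs. With two placebo patients, same-cohort incidence can only be 0, 50 or 100%, so the calculated shift would not be visible as such. That stands, and it limits the severity.

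The size is also open to challenge, and these points stand too. The AACC rate was measured 3 months after the first dose, and titres were followed only to 3 months after the last dose; neither shows positivity persisting to 48 weeks. This study tests whether new regimens reduce immunogenicity. Constant hazard suits background AEs better than the main risks: AACC infusion reactions began during or within 30 minutes of an infusion, and the extension visits include no MRI, so they add no routine ARIA detection.

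Three stronger readings are tempting, and the documents do not support them.

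- A reader might infer a general active-placebo imbalance across the study. The 48-week cap excludes completers in four of seven cohorts.
- A reader might infer that the extension belongs to the active arm and always inflates its rates. Concentration on active drug is inferred from AACC; Protocol 10.4.1 foresees patients positive at baseline, so placebo patients can qualify. For Cohort 3 the direction depends on how placebo is grouped.
- A reader might infer that the extra visits unblind relatedness judgements. Protocol 10.1 withholds potentially unblinding results from sites, and a positive titre does not prove active treatment. A visit instruction could hint at assignment, but no more can be said.

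None of this supplies the missing cut-off.

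**Conclusion.** The point holds in limited form. For completers in Cohorts 3, 6 and 7, and for early discontinuers in any cohort, the plan as written can count AEs over different lengths of time in titre-positive and other patients. That probably means longer on LY3002813 than on same-cohort placebo.

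The shift from 30% to about 49% (Cohort 3) or 39% (Part C) is effectively an upper bound. It needs equal constant hazards, 90% of active and no placebo patients positive to the cap, full-length Part C dosing and same-cohort placebo. The real effect may be far smaller.

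The 24-week against 72-week mismatch in Part A follows from the schedule alone and needs no antibody assumption. Whether Cohort 3 looks worse or better than placebo depends on a grouping that the SAP leaves unstated. Severity is minor to moderate.

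**What to change.** In SAP 4.2.7.1:

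- End the by-dose AE incidence tables at the last visit scheduled for every patient in the cohort: V13 in Cohort 3, V17 in Cohorts 1-2, V22 in Part B, V27 in Part C. Define the TEAE window in 4.4 with the same cut.
- Report AEs from titre-triggered visits in a separate listing or table. Identify them by visit type as well as date, because an early discontinuer's extension can fall before the cohort's final week. For example, a Part B last dose at Week 10 puts the cap at Week 58, before V22 at Week 72.
- For any table that sets Cohort 3 beside Cohorts 1-2 or combined Part A placebo, use a common Week 24 cut or exposure-adjusted rates.
- State how placebo is grouped in the AE tables, and reconcile the SAP's description of the extra visits with Protocol 10.4.1.

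Planned observation of completers is then equal for active and placebo within each cohort: 72 weeks in Cohorts 1, 2, 4 and 5, 24 in Cohort 3 and 84 in Cohorts 6-7.

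The cost is SAP wording and an extra listing or table; visits and data collection do not change. The downside is that late events leave the main incidence table, which is why they need their own display. A Week 24 cut also sets aside later data from Cohorts 1-2 in that one comparison; exposure-adjusted rates keep those data but lean on a roughly constant hazard.

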9.2.1. Method of Assignment to Treatment

A patient number will be assigned to each patient after the ICF is signed and dated. This identification number must appear on all patient-related documents. Assignment to treatment groups will be determined by a computer-generated random sequence within each dose cohort using an interactive web response system (IWRS).

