11.2.7. Safety Analyses

11.2.7.1. Clinical Evaluation of Safety

All investigational product and protocol procedure AEs will be listed; if the frequency of events allows, safety data will be summarized using descriptive methodology.

The incidence of symptoms for each treatment will be presented by severity and by association with investigational product, as perceived by the investigator. Symptoms reported to occur

before randomization will be distinguished from those reported as new or increased in severity during the study. Each symptom will be classified by the most suitable term from the medical regulatory dictionary.

The number of investigational product-related SAEs will be reported.

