Abbreviations: A β = amyloid-beta; ADAS-cog = Alzheimer's Disease Assessment Scale-Cognitive Subscale; ADCS-MCI-ADL24 = Alzheimer's Disease Cooperative Study-Mild Cognitive Impairment-Activities of Daily Living, 24-item questionnaire; AE = adverse event; CDR = Clinical Dementia Rating; CSF = cerebrospinal fluid; C-SSRS = Columbia Suicide Severity Rating Scale; D = day; ECG = electrocardiogram; ED = early discontinuation; EDTA = ethylene diamine tetraacetic acid; FCSRT-IR = Free and Cued Selective Reminding Test with Immediate Recall; FU = follow-up; hr = hours; IWRS = interactive web response system; LP = lumbar puncture; M = month; MMSE = Mini-Mental State Examination; MRI = magnetic resonance imaging; NTB = Neuropsychological test battery; PET = positron emission tomography; PK = pharmacokinetics; RAND = randomization; RBC = red blood cells; RNA = ribonucleic acid; SHSF = Self-Harm Supplement Form; V = visit; WBC = white blood cells.

*Approximate days and may be highly variable.

- a Patients may be admitted on Day -1, to perform these tests, at the discretion of the site. Note that the ADAS-cog and NTB testing must be separated from each other by 4 hours to avoid testing fatigue and all cognitive tests must be performed before LP if on the same day and LP must be performed no closer than 24 hours from dosing.
- b Patients will remain at the site for at least 6 hours after the end of infusion. Any patient discharged before the 24-, 48-, and 72-hour procedures will be required to return to the site for procedures at the respective time points.
- c Screening tests may occur up to 56 days before the study drug administration apart from the exceptions presented in Section 8.1.
- d Performed before dosing.
- e A single ECG will be obtained at screening and will not be transmitted to central vendor. All other ECGs will be done in triplicate and transmitted to the central vendor for storage. For visit with no specified ECG timing ("X"), the ECG should be collected close to the PK collection and should be time matched with preadmission ECGs (Visit 4).
- f If the investigator determines that suicide-related behaviors have occurred, the Lilly SHSF form will be used to collect additional information to allow for a more complete assessment of these behaviors.

- g All analytes will be measured.
- h If patient discontinues before the MRI, request that patient returns for this procedure even though all other interim study evaluations may be forgone.

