- n For the baseline LP, it may be performed no closer than 24 hours before first dosing and be part of a Day -1 admission and dosing may not proceed until patient reports at least 12 hours after resolution of symptoms of post-LP headache, if present. For Part A only, predose CSF samples by single LP should be conducted at least 3 days before dosing, because a second CSF sample will be taken approximately 3 days after dosing with study drug. Local laboratory will process CSF for cells (RBCs and WBCs, where possible) and protein and glucose, the remainder will be sent to central laboratory. CSF will be analyzed for PK (post treatment sample only), A β , tau, protein, and cell count. Additional CSF will be collected for storage, as described in Section 10.3. LPs are required for all patients and can be performed up to 11 days before dosing. However, LPs are not required for Japanese patients who are added after the planned number of patients for a cohort has already been filled. LPs should be conducted at approximately the same time as plasma PK samples, if applicable. If there is no PK drawn, LPs should be conducted at approximately the same time of day.
- o A pharmacogenetic sample will be obtained preadmission or before the first dosing. An additional sample may be taken postdose if required.
- p Performed predose and 24 hours after the start of dose. If the subject is discharged prior to the 24-hour assessments, these should also be conducted prior to discharge.
- q The numbers in the rows refer to scheduled hours postdose for sampling, measured from the start of the infusion. The “predose” collection indicates that the sample should be taken up to 30 minutes before the beginning of the infusion. The “end of infusion” collection indicates that the sample should be taken as close to the completion of the infusion as possible. On the day of dosing, postdose samples should be collected from a different arm than was used to administer study drug. If no specific time point is indicated (“X”), a single sample will be collected as close as possible to the dosing time on the previous infusion day.

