#### **4.4. Clinical Trial Registry Analysis Plan and DSUR**

Additional analyses will be performed for the purpose of fulfilling the Clinical Trial Registry (CTR) requirements.

Analyses provided for the CTR requirements include the following:

- Summary of AEs, provided as a dataset which will be converted to an XML file. Both SAEs and 'Other' AEs will be summarized: by treatment group, by MedDRA PT.
- An AE is considered 'Serious' whether or not it is a treatment emergent adverse event (TEAE).
- An AE is considered in the 'Other' category if it is both a TEAE and is not serious. For each SAE and 'Other' AE, for each term and treatment group, the following will be provided:
  - the number of participants at risk of an event
  - the number of participants who experienced each event term
  - the number of events experienced.
- Consistent with [www.ClinicalTrials.gov](http://www.ClinicalTrials.gov) requirements, 'Other' AEs that occur in fewer than 5% of patients/subjects in every treatment group may not be included if a 5% threshold is chosen (5% is the minimum threshold).

- Adverse event reporting is consistent with other document disclosures for example, the CSR, manuscripts, and so forth. AE reporting is consistent with other document disclosures for example, the CSR, manuscripts, and so forth.

The following reports will be included the DSUR:

- [1] Estimated cumulative subject exposure,
- [2] Cumulative exposure to investigational drug by demographic characteristics for ongoing unblinded clinical trials and completed clinical trials,
- [3] Exposure information for ongoing clinical trials and clinical trials that completed during the reporting period
- [4] Listing of subjects who died during the DSUR period,
- [5] Discontinuations due to an AE during the DSUR Period.

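### Symptoms are separated at randomisation rather than at first infusion, so events without any exposure can enter the incidence shown for a dose group.

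*SAP*

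**What the plan says.** SAP 4.2.7.1 sets two classes of symptom: "Symptoms reported to occur before randomization will be distinguished from those reported as new or increased in severity during the study". Protocol 11.2.7.1 uses the same cut: "before randomization will be distinguished from those reported as new or increased in severity during the study". The tabulation is by dose: "The incidence of symptoms for each IV dose will be presented by severity and by association with investigational product, as perceived by the investigator". The same SAP section adds: "All investigational product and protocol procedure AEs will be listed".

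SAP 4.4 classifies non-serious events for the registry with a different term: "An AE is considered in the 'Other' category if it is both a TEAE and is not serious". Protocol Section 4 expands the abbreviation TEAE, but neither document says when treatment emergence starts.

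On the time of randomisation, Protocol 9.2.1 gives only the method: "Assignment to treatment groups will be determined by a computer-generated random sequence within each dose cohort using an interactive web response system (IWRS". It names no visit or day. The schedule in Attachment 1 has a Rand label in the Part C tables only, explained in the abbreviations as "RAND = randomization". On the baseline lumbar puncture (LP), footnote n of Attachment 1 says: "LPs are required for all patients and can be performed up to 11 days before dosing".

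**The concern.** Randomisation assigns a patient to a dose; the first infusion exposes the patient to it. A safety incidence by dose should start at the second of these. With the cut at the first, an event that began and ended before any infusion is counted as new or worsened for a dose group.

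Safety is a secondary objective, and the cohorts are planned with 6 or 9 active patients each, so a single misplaced event visibly changes a percentage. The interval may also hold an invasive procedure with its own symptoms. Headache after an LP is the obvious one, and Protocol 9.5.1.3 also lists headache among the symptoms reported with ARIA-E.

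**Working it through.** The plan gives no figure to reproduce. The check sets the rules side by side and then gives the weight of one event.

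**1. Which class does a pre-infusion event fall in?** The rule has two classes: before randomisation, and new or worse during the study. An event after randomisation but before the first infusion is not in the first class, so it falls in the second and is shown under the assigned dose.

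**2. Can patients with no exposure be included?** Yes, on three statements together:
- Protocol Section 4 defines enrolment as assignment to a treatment.
- SAP 4.2.1 and Protocol 11.2.1 base safety analyses on all enrolled patients. The PK/PD set, by contrast, requires at least one dose.
- Protocol 8.2 provides for randomised patients who discontinue without having received product.

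This step does not depend on the LP or on the day of randomisation.

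**3. What anchor do the other safety rules use?** Protocol 10.6.1 records adverse events from consent onward and requires reporting of all events after the first dose. Protocol 10.6.2 starts SAE collection once product has been received. Pre-dose events will therefore be recorded and need a class, and the neighbouring rules already turn on the first dose.

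**4. Does the interval contain the baseline LP?** The LP belongs to Visit 4, nominally Day -4 with a tolerance of 4 days; the first dose is at Visit 5, Day 1. Attachment 1 allows the LP from 11 days to 24 hours before dosing, and at least 3 days before in Part A.
- Randomisation at Visit 4 before the LP: the interval is about 4 days (4 - 4 = 0 to 4 + 4 = 8 with the tolerance) and contains the LP.
- Randomisation at Visit 4 after the LP: the LP is outside, but a symptom of later onset could be inside.
- Randomisation on Day 1: the interval is hours long and the LP is outside.

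The evidence does not choose among these:
- The Rand label stands over Visit 4 in one Part C table. In the continuation it is broken across Visits 4 and 5, and other entries in these tables are out of column. Parts A and B have no label.
- SAP 4.2.5.2 takes the cognitive baseline at Visit 3 or before randomisation, while ADAS-cog, NTB and the ADL scale are scheduled pre-dose only at Visit 4. Visit 4 cognitive testing can therefore precede randomisation.
- That does not place the LP, because footnote a puts cognitive testing before the LP when both are on one day.

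**5. Weight of one misplaced patient.**
- Single-dose active group: 1/6 = 16.7 percentage points.
- Multiple-dose active group: 1/9 = 11.1 percentage points.

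**The case against.** The strongest case against the point is that it matters little in practice.

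- **The LP may lie outside the interval.** The only marker for randomisation is a label whose column is uncertain, in one of three parts of the study. Protocol 7.1.1 describes Visit 4 testing and the LP under screening. An LP at 11 days also lies outside the nominal Visit 4 range of up to 8 days. This stands: the LP is a possibility, not a finding.
- **The rule does not attribute these events to drug.** It says during the study. Relatedness to product is tabulated, procedure events are listed, and investigators assess the two relations separately under Protocol 10.6.1. This stands and limits the harm. It does not correct the by-dose incidence itself.
- **Headache counts do not decide ARIA-E.** ARIA-E is assessed by a blinded central MRI read and shift tables. Footnote n also holds dosing until at least 12 hours after post-LP headache symptoms have resolved. Both stand. But a headache that has resolved before exposure is exactly the event that should not be shown under a dose.
- **A first-infusion cut leaves other LP symptoms in.** Part A has a second LP about 3 days after dosing, and Parts B and C have one after 24 weeks of dosing. True: only procedure attribution separates those.

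A reader might also infer that the safety tables and the registry tables use contradictory cut points. The documents do not show that. TEAE is given no start point, so the defect in SAP 4.4 is an undefined term. What can be said is that the consistency with other disclosures stated there cannot be checked.

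None of these objections makes randomisation as good a cut as first infusion.

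**Conclusion.** The point holds as a defect in a stated rule. Both documents cut at randomisation and present incidence by dose, and the safety population can include patients who were never dosed, so events without exposure can enter dose-group incidence. If randomisation is at Visit 4, baseline LP events may be among them. They would arise in active and placebo groups alike, so they add background rather than a directional bias.

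The size cannot be estimated from the documents, which give neither the day of randomisation nor a rate of pre-dose symptoms. A reader might be tempted to assume that 5% to 30% of patients have a pre-dose LP symptom and to conclude that 54 × 0.05 = 2.7 to 54 × 0.30 = 16.2 of the planned 54 active patients (3 × 6 + 4 × 9) are misplaced, with a chance of at least one in a 9-patient group of 1 - 0.95^9 = 0.37 to 1 - 0.70^9 = 0.96. The arithmetic is right, but the documents do not support the conclusion. The rate is assumed, every LP is taken to follow randomisation, and a Part C label is applied to all parts. Part C alone has 2 × 9 = 18 active patients, which on the same assumed rate gives 0.9 to 5.4.

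It would also go too far to say that these events are counted as occurring on study drug.

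**What to change.** In SAP 4.2.7.1 and Protocol 11.2.7.1, define treatment-emergent as first occurring or worsening after the start of the first infusion. Tabulate events from randomisation to first infusion separately as pre-treatment; a patient who is never dosed then contributes no emergent event. Apply the same definition to the TEAE term in SAP 4.4.

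It would also help to state when randomisation occurs relative to the Visit 4 LP, although the first-infusion cut is correct wherever it falls.

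The cost is a sentence or two in each document. Protocol 9.2 already requires actual dose times in the case report form, so no new data are needed. Label: free improvement.
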